6.4. Patient Disposition

All patient discontinuation data collected on the eCRF will be listed, including the extent of the patient participation in the study. If known, a reason for their discontinuation from treatment and from study will be listed and summarized. All patients entered in the study will be included in the summary and listing.

All significant protocol violations will be listed by pre-determined categories (eg, inclusion/exclusion criteria, errors/missing data in the informed consent process, noncompliance with protocol procedures, patients continuing after meeting withdrawal criteria, or other violations as recorded on eCRFs or monitoring reports).

6.5. Patient Characteristics

Patient characteristics will include a summary and/or listing by cohort in Phase 1b and histology cohort in Phase 2 of the following:

• Patient demographics including (for example) age, sex, ethnicity/race, weight and change in weight from baseline, and screening height will be reported.

- baseline disease characteristics and in Phase 2, including histology
- prior disease-related therapies
- concomitant medications

6.5.1. Demographics

Patient demographics including age, sex, ethnicity, race, height at baseline, weight at baseline, body mass index (BMI) at baseline will be summarized for all treated patients using descriptive statistics and listed in a data listing.

6.5.2. Baseline Disease Characteristics

Eastern Cooperative Oncology Group (ECOG) performance status, initial pathological diagnosis, basis for initial diagnosis and disease stage will be summarized for all treated patients using descriptive statistics and listed in a data listing.

6.5.3. Pre-existing Conditions and Medical History

Medical history (MH) conditions are historical illnesses, pre-existing conditions and relevant surgeries or other procedures that started prior to signing the informed consent document. All MH conditions will be coded using the MedDRA dictionary and by using the Common Terminology Criteria for Adverse Events (CTCAE).

A historical condition is a MH condition that has ended prior to the date of informed consent.

A **preexisting condition** is a MH condition that is either ongoing or has ended on or after the date of informed consent.

Historical and preexisting conditions will be summarized and listed for all treated patients. Summaries will be presented by System Organ Class (SOC) and by decreasing frequency of MedDRA Preferred Term (PT) within SOC.

The MH verbatim and MedDRA PT will be listed along with start and end dates. Additionally, CTCAE severity grade will be listed for preexisting conditions.

6.5.4. Prior Therapies

Prior therapies, including systemic therapy, radiotherapies, and surgeries will be listed for all treated patients.

The number of patients with prior therapies will be reported by category of prior therapy, as well as by reasons for regimen. Additionally, the number of prior regimens for prior systemic therapy will be reported.

6.6. Concomitant Therapy

All medications entered on the CRF will be coded according to the current WHO drug dictionary.

Concomitant medications will be listed and summarized for all treated patients. The WHO classification, start and end dates, and indication for which the medication was taken will be included in the listing.

Palliative radiotherapy treatment during treatment will also be summarized.

Post discontinuation therapy will be listed and summarized.

6.7. Efficacy Analyses

For the Phase 1b portion of the trial, one of the exploratory objectives is to document the preliminary antitumour activity of the combination of galunisertib and nivolumab.

For the Phase 2 portion of the trial, one of the secondary objectives is to evaluate preliminary antitumour activity of the combination including PFS, ORR, duration of response, and time to response of the combination of galunisertib and nivolumab in patients with NSCLC or HCC.

6.7.1. Endpoint Definitions

The following efficacy endpoints will be determined:

Overall response rate (ORR) is the proportion of patients who achieved a complete response (CR) or partial response (PR) as their best overall response out of all patients treated set.

Tumour responses will be assessed using the CCI guidelines for patients with NSCLC, HCC, and tumours other than glioblastoma.

Tumor responses will be assessed using the CCI guidelines for patients with glioblastoma.

Best response is determined from a sequence of responses assessed for each patient per the respective guidelines.

Disease Control Rate (DCR) is defined as the proportion of treated patients achieving a best overall response of complete response (CR), partial response (PR), or stable disease (SD) as their best overall response out of all patients treated set.

Change in tumour size (CTS) will be assessed in each patient using radiographic imaging. This endpoint will be based on tumour measurements collected by the centers according to the applicable guidelines.

- For patients with NSCLC, HCC, and tumours other than glioblastoma, tumour size is defined as the sum of the largest diameter for each target lesions at each tumour evaluation for CCI
- For patients with glioblastoma, tumor size is defined as the sum of the largest diameter for each measurable lesion at each tumor evaluation for **COLO**. Change in tumour size is defined as the percent change in tumour size from the baseline evaluation to the evaluation at the each tumour evaluation, only including the tumors present at baseline.

The change in tumour size corresponding to the best response for each patient will be represented in waterfall plots.

Time to Response is defined only for responders. It is measured from the date of first study treatment to the first documented response.

Duration of Response will be calculated for ORR and is defined only for responders. It is measured from the date of documented response to the date of first progression of disease or the date of death due to any cause, whichever is earlier. For each patient who is not known to have died or to have had a progression of disease at the cut-off date, duration of response will be censored at the date of last objective response assessment prior to the date of any subsequent systemic anticancer therapy.

Progression-free survival (PFS) is defined as the time from the date of first study treatment to the first date of documented progression or death due to any cause, whichever occurs first. For patients who are not known to have died or progressed as of the cut-off date, PFS time will be censored at the date of the last progression-free disease assessment prior to the date of any subsequent anticancer therapy.

Overall Survival (OS) is defined as the time from the date of first study treatment to the date of death from any cause. For each patient who is not known to have died as of the cut-off date, OS will be censored for that analysis at the date of last contact prior to the data inclusion cutoff date (contacts considered in the determination of last contact date include AE date, lesion assessment date, visit date, and last known alive date).

The detailed algorithm for the censoring rules will be described in the analysis dataset requirements (Adam requirements).

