Treatment decisions related to patient management and whether to treat a patient with advanced refractory solid tumours with additional cycles of study therapy will be based on RECIST version 1.1 for all study patients except patients with glioblastoma, for whom treatment decisions will be based on RANO criteria.

[figure not shown]
At the sponsor's discretion, scans and measurements may be collected and reviewed by independent radiologists using RECIST version 1.1/RANO criteria at a later date, or at any time during the study.

The planned duration of treatment is not fixed; patients will remain on study treatment until they fulfil 1 of the criteria for study discontinuation ([Section 6.3](#)). Patients demonstrating a benefit from treatment may continue on combination therapy if the patient and investigator feel that the patient is benefiting from treatment. If a patient experiences an AE that requires the patient be discontinued from 1 of the 2 study drugs, the patient should continue on the other study drug

(Section 7.2.4). Landmark analysis of all study patients will occur at 6, 12, and 18 months, and OS will be assessed at the end of trial.

Patients who have discontinued from combination treatment will enter the Safety Follow-Up period with visits at approximately 30 and 100 days. If the patient has only discontinued from 1 of the 2 study drugs, the patient will continue on treatment until they discontinue from the second drug, at which time they will enter the Safety Follow-Up period as noted above. If patients have discontinued treatment for reasons other than disease progression, tumour assessments should continue every 8 weeks until disease progression occurs, initiation of a new anticancer therapy, the patient dies or is lost to follow-up. Patients will be followed for survival approximately every 12 weeks (± 7 days) until death or end of trial. This follow-up may occur through a phone call, email, or visit by the patient or the patient's caretaker.

Refer to [Attachment 1](#) for the study schedule.

Abbreviations: approx = approximately; BID = twice daily; IV = intravenous; HCC = hepatocellular carcinoma; n = number of patients; NSCLC = non-small cell lung cancer; Q2W = every other week; QD = daily; TBD = to be determined.

Figure JBEF.6.1. Study H9H-MC-JBEF design.

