8.3. Efficacy Evaluations

The following efficacy measures will be determined:

- ORR and best overall response, time to response, duration of response, and PFS
 - using RECIST version 1.1 ([Attachment 8](#)) for patients with NSCLC, HCC, and tumours other than glioblastoma
 - using RANO (see [Attachment 9](#)) for patients with glioblastoma
- survival at 6, 12, and 18 months following the start of treatment
- OS determined from the date of first treatment until death due to any cause
- change in ECOG performance status

Efficacy measures will be assessed as noted in [Attachment 1](#). Disease assessment with CT and/or MRI, as appropriate, will be performed at baseline and every 8 weeks until disease progression per RECIST version 1.1 or until patients withdraw from the study. For patients who are being treated beyond initial progression, these patients should remain on study treatment until the next assessment period. Patients who are treated beyond progression will be evaluated on an 8 (nonglioblastoma patients)- or 12 (glioblastoma patients)-week basis to determine whether they should continue on treatment. The use of MRI is mandatory to determine tumour response when using RANO criteria. Brain imaging should be performed as clinically indicated. At the sponsor's discretion, scans and measurements may be collected and reviewed by independent radiologists using RECIST version 1.1/RANO criteria at a later date, or at any time during the study.

To confirm objective responses, all lesions should be radiologically assessed, and the same radiologic method used for the initial response determination should be repeated at least 4 weeks following the initial observation of an objective response, using the same method that was used at baseline. If a patient is discontinued from the study, repeat radiology assessments may be omitted if clear clinical signs of PD are present.

To facilitate this effort the radiologist reading the baseline imaging study is asked to provide in the baseline report or in a supplemental report a comparison of the size of target lesions and nodes reported in the baseline study with the size of these same lesions and nodes, if present, in the reference study. The report should also make note of the date of the preceding referenced study. Reference study data provided in the radiologist's report should be entered into the eCRF by the investigator's staff.

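### SAP 6.7.1 censors PFS and duration of response at new anticancer therapy only when no later event is known, so a switcher's place in the Kaplan-Meier curve depends on later outcome

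*SAP*

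**What the plan says.** **Event.** SAP 6.7.1 runs PFS from first study treatment "to the first date of documented progression or death due to any cause, whichever occurs first". New anticancer therapy is not an event, and nothing in the readable text stops events from counting after it starts.

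**PFS censoring.** The rule opens with a condition: "For patients who are not known to have died or progressed as of the cut-off date". Only for those patients does it add that "PFS time will be censored at the date of the last progression-free disease assessment prior to the date of any subsequent anticancer therapy".

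**DOR censoring.** The condition is the same, "For each patient who is not known to have died or to have had a progression of disease at the cut-off date", and then "duration of response will be censored at the date of last objective response assessment prior to the date of any subsequent systemic anticancer therapy". PFS refers to any anticancer therapy, DOR to systemic therapy only.

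**Follow-up.** For patients who stop treatment without progression, protocol 6.2 says "tumour assessments should continue every 8 weeks until disease progression occurs, initiation of a new anticancer therapy", death or loss to follow-up. The same section adds "Patients will be followed for survival approximately every 12 weeks", until death or end of trial. Protocol 8.3 describes disease assessment "every 8 weeks until disease progression per RECIST version 1.1 or until patients withdraw from the study" and does not list new therapy as a reason to stop.

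**Analysis.** SAP 6.7.2 uses Kaplan-Meier for PFS, DOR and OS. SAP 6.7.1 leaves the detailed censoring algorithm to the analysis dataset requirements, which are not among the documents.

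**The concern.** Two patients with the same history up to a switch of therapy are handled differently because of what happens afterwards. The one who later dies stays in the risk set, counted as progression-free, until death. The one who survives is removed back at the last scan before the switch. Kaplan-Meier assumes that leaving the risk set carries no information about later outcome, and this rule breaks that assumption by construction.

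The follow-up plan makes it matter. If scans stop at new therapy and survival contact goes on, progression after the switch is mostly unseen while death is recorded. Switchers who die then contribute long progression-free times that nobody observed. At stake is how far the PFS and DOR curves, both Phase 2 secondary endpoints, can be trusted in each cohort.

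**Working it through.** The documents give no PFS target and no expected share of patients who switch before progression, so there is no figure in the plan to reproduce. The check has two parts.

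**1. One patient under the literal rule.** New therapy starts at 3.0 months. The last scan before it is at 8 weeks, which is 56 / 30.44 = 1.84 months.
- Death at 11 months: event at 11.0.
- Alive at a 12-month cut-off: censored at 1.84.

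Whether this patient is at risk between 1.84 and 11 months is decided by the later outcome.

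**2. Size, by simulation with 400,000 patients per scenario.**

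From the documents: 8-weekly scans, scans stopping at new therapy, deaths still known, Kaplan-Meier.

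Assumed: exponential time to progression with median *m* of 3 or 5 months; median 6 months from progression to death; 5, 15 or 35% switching before true progression, unrelated to prognosis; cut-off 12 to 24 months after first dose. Because documentation waits for a scan, nominal 35% at *m* = 3 corresponds to about 42% switching before *documented* progression.

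Reference value: progression is documented at the next scan, so at 6 months the last scan is the third, at 3 × 1.84 = 5.52 months, and PFS(6) ≈ 2^(−5.52/*m*). This gives 2^(−1.84) = 27.9% for *m* = 3 and 2^(−1.104) = 46.5% for *m* = 5. The simulated references agree (27.8 to 27.9% and 46.5%).

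| *m* (months) | Nominal switching | Reference 6-month PFS | SAP rule, scans stopped | Difference (points) |
|---|---|---|---|---|
| 3 | 5% | 27.8% | 28.9% | +1.1 |
| 3 | 15% | 27.8% | 31.6% | +3.8 |
| 3 | 35% | 27.9% | 38.6% | +10.7 |
| 5 | 5% | 46.5% | 46.9% | +0.4 |
| 5 | 15% | 46.5% | 47.9% | +1.4 |
| 5 | 35% | 46.5% | 50.7% | +4.2 |

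A separate simulation with *m* = 4 and an 18 to 30 month cut-off agrees in direction: 39.2% against 38.2% when 6% switch before documented progression, and 45.5% against 38.4% when 34% do.

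**What changes the answer**
- *Early cut-off (6 to 12 months), scans stopped.* Few later deaths are known, so almost every switcher is censored. The error is about 1 point or less when switching is unrelated to prognosis (largest value 1.2), and at most about 1.4 points in the *m* = 4 runs where faster progressors switched more.
- *Progression after the switch captured.* Switchers who progress or die count, and only event-free switchers are cut back, so the error turns downward. It is 0.3 to 3.8 points over 15 to 35% switching. For *m* = 3 at 35%: 27.1% against 27.9% at 6 months and 6.2% against 7.8% at 12 months.
- *Median PFS.* It rose by about 0.9 month at 35% switching with 12 to 24 months of follow-up, and did not move in any *m* = 4 scenario.
- *Censoring every switcher.* This returns the reference within 0.3 point if switching is unrelated to prognosis. If faster progressors switch more, it leaves +1.4 points in one model (39.5% against 38.1%), and +4 to +6 points when they switch three times as often.

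DOR was not simulated.

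**The case against.** **The algorithm is deferred.** The analysis dataset requirements may settle the matter, and they cannot be seen here. That limits what can be said about the eventual programming. It does not remove the point: which events count is part of the endpoint definition, and the approved SAP already states a conditional rule. The later document would have to implement that rule or contradict it.

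**Scans may not stop.** Protocol 8.3 does not name new therapy as a stop. Protocol 7.2.5 asks for efforts to document objective progression after treatment ends, and 8.1.2.2.3 wants follow-up assessments completed before a new therapy begins. Some progressions would then be documented, before or after the switch. This stands. A reader might infer that PFS will be overstated, but the documents do not support a fixed direction: the sign depends on how much is collected after the switch.

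**The switching rate is assumed.** This also stands. Treatment beyond progression is permitted (protocol 7.2.5), which argues against assuming high rates of switching before progression, so the upper end of the table is an extreme.

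**Uniform censoring is not neutral.** Agreed. A reader might infer that it recovers the true curve, but that holds only if switching is unrelated to prognosis.

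**Palliative radiotherapy.** A reader might infer that it would trigger the PFS rule and not the DOR rule. Protocol 7.5 allows it separately and describes antineoplastic radiation as extensive and nonpalliative, so this is a minor wording mismatch.

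**Consequence.** With 25 patients, the 95% half-width for 6-month PFS is about 1.96 × √(0.279 × 0.721 / 25) = 18 points, or 1.96 × √(0.465 × 0.535 / 25) = 20 points. Both exceed every error above. But an interval describes sampling error and does not allow for bias.

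**Conclusion.** The point holds as a defect in a stated rule. Under SAP 6.7.1 the censoring of a patient who switches therapy before progression depends on whether death or progression is later known, and Kaplan-Meier does not allow that.

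The size is conditional. With scans stopped, 5 to 35% nominal switching unrelated to prognosis and 12 to 24 months of follow-up, 6-month PFS is overstated by about 0.4 to 11 points. The error is about 1 point or less with a 6 to 12 month cut-off and scans stopped, and it is downward if post-switch progression is captured. None of the switching rates or medians comes from the documents.

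DOR carries the same conditional wording and so the same fault, but no size can be given for it.

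Severity is low to moderate. PFS and DOR are secondary, single-arm estimates in about 25 patients per cohort. A reader might infer that cohort expansion is affected, but SAP 5.2 and 6.12 base expansion on responses (or survival for HCC), not on PFS or DOR. The primary safety objective is untouched.

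**What to change.** In SAP 6.7.1:
- State one rule that does not depend on later outcome. If new anticancer therapy starts before documented progression or death, censor PFS and DOR at the last adequate tumour assessment before that start, whatever happens later.
- Report an all-events version, counting every known progression and death, as a sensitivity analysis. It is needed because uniform censoring is unbiased only if switching is unrelated to prognosis.
- Use one definition of anticancer therapy for both endpoints, saying whether permitted palliative radiotherapy counts.
- Carry the same rule into the analysis dataset requirements.

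In the protocol, reconcile sections 6.2 and 8.3 on when scans stop, since the direction of any error depends on it.

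The cost is SAP wording and one derivation change. SAP 6.6 already lists and summarises post-discontinuation therapy, so the SAP change needs no new data. The downside is that a few late deaths no longer count as PFS events in the main analysis; the sensitivity analysis retains them.

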6.7.2. Analysis Methods

Individual best overall response, time to and duration of response, PFS, and OS will be listed and summarised by dose for the Phase 1b and by disease cohort for the Phase 2. Additional analyses may be performed as deemed appropriate depending on the final number of patients treated in each dose cohort.

For the Phase 2 portion of the study, the following analyses will be performed:

- Rates including ORR and DCR will be computed for each cohort and the estimates will be reported with exact 95% confidence intervals.
- Time to events variables including PFS, DOR, and OS will be analysed using the Kaplan-Meier method (Kaplan and Meier 1958). Survival curves will be used to summarize the data and medians will be reported with the 95% confidence intervals for each cohort. In addition, for each time to event variable, survival rates at adequate time points may be reported (eg. 6, 12, 18 months).
- Time-to-response will be summarised using descriptive statistics by cohort.
- Individual changes in the tumour size over time will be presented graphically by tumour type using spider plots. The change in tumour size corresponding to the best response

based on target lesions (for ^{CCI} for each patient will be represented in waterfall plots by cohort.

 ECOG performance status over time will be presented graphically to explore changes over time.

To understand the impact of baseline biomarkers on efficacy, the following analyses may be considered:

- For the NSCLC cohort, efficacy endpoints may be evaluated by adjusting for baseline PD-L1 expression and serum TGFβ-1 levels.
- For the HCC cohort, efficacy endpoints may be evaluated by adjusting for serum AFP and TGFβ-1 levels and tumour PD-L1 expression.

In addition, sensitivity exploratory analyses may be conducted using arrests.

6.8. Bioanalytical and Pharmacokinetic/Pharmacodynamics Methods

6.8.1. Pharmacokinetics

Lilly PK will perform the PK analyses per the separate PK/PD analysis plan, except as indicated below.

Pharmacokinetics analyses will be conducted on patients who have received at least 1 dose of the study drug and have had samples collected. For galunisertib, population apparent clearance, volume of distribution, and exposure are steady state for galunisertib will be calculated. For nivolumab, C_{min} concentrations will be reported. If data warrants, dose proportionality of galunisertib when coadministered with nivolumab during Phase 1b may be assessed based on a power model. Nivolumab C_{min} concentration in Phase 1b will be tabulated by summary statistics.

Providing that the data allow (ie, PK parameters are available for more than 2 dose levels), the PK parameter estimates for galunisertib may be evaluated statistically. The degree of dose proportionality will be assessed by fitting the power model to the log transformed PK parameters. Different fold-ranges of doses will be chosen to provide estimates of ratios of dosenormalized geometric means, depending on the actual range of doses tested in the study (Smith et al. 2000).

In the event that the power model is not a good representation of the data over the entire dose range tested, alternative models may be investigated.

